## 7.4.1 Atezolizumab

Patients will receive Atezolizumab 840 mg IV, on Days 1 and 15 of a 28-days cycle, and its first dose will be started on Cycle 1 Day 15. Administration of Atezolizumab will be performed in a setting with emergency medical facilities and staff who are trained to monitor for and respond to medical emergencies. Atezolizumab infusions will be administered per the instructions outlined below:

## First Infusion:

- No premedication is administered.
- Record patient's vital signs (heart rate, respiratory rate, blood pressure, and temperature) within 60 minutes before starting infusion.
- Infuse 14 mL Atezolizumab (840 mg) in 250 mL NaCl) over 60 (± 15) minutes.
- Record patient's vital signs (heart rate, respiratory rate, blood pressure, and temperature) during and after the infusion if clinically indicated
- Patients will be informed about the possibility of delayed symptoms following infusion and instructed to contact their study physician if they develop such symptoms.

## Subsequent Infusions:

- If patient experienced infusion-related reaction during any previous infusion. premedication with antihistamines may be administered for Cycles ≥2 at the discretion of the treating physician.
- Record patient's vital signs (heart rate, respiratory rate, blood pressure, and temperature) within 60 minutes before starting infusion.
- If the patient tolerated the first infusion well without infusion-associated adverse events, the second infusion may be administered over 30 (± 10) minutes. • If no reaction occurs, subsequent infusions may be administered over 30 (± 10) minutes Continue to record vital signs within 60 minutes before starting infusion and during and after the infusion if clinically indicated.
- If the patient had an infusion-related reaction during the previous infusion, the subsequent infusion must be administered over 60 (± 15) minutes. Record patient's vital signs (heart rate, respiratory rate, blood pressure, and temperature) during and after the infusion if clinically indicated.

## 7.4.2 Cobimetinib

Patients will receive and self-administer Cobimetinib at 60 mg PO daily, on Days 1 – 21 of a 28days cycle.

Patients will be given a sufficient number of tablets to last until the next visit. In some cases, extra tablets may be dispensed if there is a possibility that the patient's next visit may be delayed (e.g., due to holiday, inclement weather, or distance of patient's home from study center).

Study drugs should be taken at approximately the same time each day, preferably in the morning, and no earlier than 1 hour and no later than 4 hours after the scheduled time. Each dose of Cobimetinib should be taken with a glass of water. Cobimetinib may be dosed with or without food. Cobimetinib tablets should never be chewed, cut, or crushed.

If a dose is missed (i.e., not taken within 4 hours after the scheduled dosing time), the patient should resume dosing with the next scheduled dose. Missed or vomited doses will not be made up. These events should be noted in the medication diary.

Patients will be asked to record the time and date they take each dose in a medication diary (located in the supplemental packet). Patients will also be given instructions for selfadministration as to the number and strength of the tablets to take. Patients will be instructed to bring all unused tablets and their medication diary to each study visit for assessment of compliance and medication disposal.

## 7.4.3 Idasanutlin

Patients will receive and self-administer Idasanutlin at (TBD) mg PO daily, on Days 1 – 5 of a 28days cycle.

Patients will be given a sufficient number of tablets to last until the next visit. In some cases, extra tablets may be dispensed if there is a possibility that the patient's next visit may be delayed (e.g., due to holiday, inclement weather, or distance of patient's home from study center).

Study drugs should be taken at approximately the same time each day, preferably in the morning, and no earlier than 1 hour and no later than 4 hours after the scheduled time. Each dose of Idasanutlin should be taken with a glass of water. Idasanutlin may be dosed with or without food. Idasanutlin tablets should never be chewed, cut, or crushed.

If a dose is missed (i.e., not taken within 4 hours after the scheduled dosing time), the patient should resume dosing with the next scheduled dose. Missed or vomited doses will not be made up. These events should be noted in the medication diary.

Patients will be asked to record the time and date they take each dose in a medication diary (located in the supplemental packet). Patients will also be given instructions for selfadministration as to the number and strength of the tablets to take. Patients will be instructed to bring all unused tablets and their medication diary to each study visit for assessment of compliance and medication disposal.

# 7.5. Definition of Dose-Limiting Toxicity (DLT) – for patients on idasanutlin armonly

Any of the following events that occur during cycle 1 (first 6 weeks) will be considered a DLT when classified as possibly, probably or definitively related to study treatment (according to NCI CTEP Adverse Event Reporting Requirements). Apart from the criteria listed below, if a lower grade AE leads to a dose interruption of more than 14 consecutive days of study drugs for the first 4 weeks of Cycle 1, this AE will be considered a DLT; patients must receive at least 75% of study drug during cycle 1 in order to be evaluable for the DLT observation period. Whenever a patient experiences toxicity that fulfills the criteria for a DLT, treatment with the study drug responsible for the toxicity will be interrupted (patient may continue the remainder study drugs) and the toxicity will be followed up. The Protocol Chair must be notified immediately of any DLT:

TOXICITY	DLT CRITERIA			
	Anemia CTCAE Grade ≥ 3 > 14 consecutive days			
	Febrile neutropenia CTCAE Grade ≥ 3			
5	ANC CTCAE Grade 3 for > 14 consecutive days			
Blood and lymphatic system disorders	ANC CTCAE Grade 4			
system disorders	Platelet count CTCAE Grade 3 for > 7 consecutive days and/or with signs of bleeding			
	Platelet count CTCAE Grade 4			
Ocular diserders	CTCAE Grade ≥ 2 for > 14 days			
Ocular disorders	CTCAE Grade ≥ 3			
General disorders and administration site conditions	Fatigue CTCAE Grade 3 for > 14 consecutive days			
Skin and subcutaneous tissue disorders	Skin, mucosal or nail toxicity CTCAE Grade ≥ 3 for > 14 consecutive days despite treatment			
GI disorders a	Diarrhea CTCAE Grade ≥ 3 for ≥ 48 hrs, despite the use of anti- diarrhea therapy			
Gi disorders*	Nausea/vomiting CTCAE Grade ≥ 3 for ≥ 48 hrs, despite the use of anti-emetic therapy			

TOXICITY	DLT CRITERIA			
	Constipation CTCAE Grade ≥ 3 for ≥ 48 hrs, despite the use of anti-constipation therapy			
	Blood bilirubin c CTCAE Grade 2 for > 7 consecutive days			
	Blood bilirubin c CTCAE Grade ≥ 3			
Investigations b	AST or ALT CTCAE Grade ≥ 3 in conjunction with blood bilirubin c CTCAE Grade ≥ 2 of any duration			
	AST or ALT CTCAE Grade 3 for > 7 consecutive days			
	AST or ALT CTCAE Grade 4			
	Alkaline phosphatase CTCAE Grade 4			
	Any other CTCAE ≥ Grade 3 toxicity except for:			
Other hematologic and non-hematologic	Decreased lymphocyte count [lymphopenia] that is not clinically significant			
toxicities	Grade 3 fatigue for less than 7 days			
	
 
Grade 3 diarrhea, nausea/ vomiting, or constipation for less or equal to 48 hours with appropriate supportive medication
 
			

a Patients will not initially receive prophylactic treatment for nausea/vomiting during Cycle 1. However, prophylactic treatment may be initiated in all patients at the dose level where these toxicities have been observed and in all further patients if at least 1 patient has experienced nausea/vomiting CTCAE Grade ≥ 3 or if at least 2 patients experienced nausea/vomiting CTCAE Grade ≥ 2. However, anti-emetics may be applied for treatment if the patient has experienced nausea/vomiting CTCAE Grade ≥ 1 at the discretion of the treating physician.

b For any hepatic toxicity CTCAE Grade 4, or CTCAE Grade 3 that does not resolve within 7 days to CTCAE Grade ≤ 1 (or CTCAE Grade ≤ 2 if liver infiltration with tumor present), an abdominal CT scan should be performed to assess if it is related to disease progression.

Apart from the criteria listed above, if a lower grade AE leads to a dose interruption of more than 14 consecutive days of Idasanutlin, this AE may be considered as DLT (the determination will be based on clinical significance and patient risk; discussion with the Protocol Chair will determine if the event should or should not count as a DLT).

Patients whose treatment is interrupted or permanently discontinued due to an AE or clinically significant laboratory value, must be followed as outlined in the table below, at least once a week for 4 weeks, and subsequently at 4-week intervals, until resolution or stabilization of the event, whichever comes first. Patients that require a dose delay of > 28 days due to a cause unrelated to study participation will have the opportunity to continue study if deemed eligible to do so by the Protocol Chair of the study.

<sup>c Refers to total bilirubin.

Hematology	If 2: CTCAE grade 3 neutropenia, anemia or thrombocytopenia have been demonstrated, these parameters must be repeated at least once a week until resolution to s CTCAE grade 1 to allow for initiation of re-treatment.

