# 7.6. Definition of Maximum Tolerated Dose (MTD) – for patients on idasanutlin arm only

The MTD will be defined as the highest dose tested in which a DLT is experienced by 0 out of 3 or 1 out of 6 patients among the dose levels. The first cohort of patients (3 patients) will be started at dose level 1, and each patient will be observed for 6 weeks on the specified dose:

If no patient in the first cohort of 3 experiences a DLT, accrual will continue to test the next dose level
If 1 patient experiences a DLT any given cohort/ dose level, an additional cohort of 3 patients will be treated at the same dose level
If 1 patient has a DLT out of 6 patients treated at this same dose, accrual will continue to test the next dose level
If 2 or more patients in 3 or 6 patients treated at a given dose experience DLT, the dose will be de-escalated to the next lower dose level. If the current dose level is at -1, the regimen will be considered too toxic and the corresponding cohort within the study will be discontinued
If 0 out of 3 or 1 out of 6 patients has a DLT treated at dose level 3, accrual will continue to the phase II portion of the study

No new cohort of patients will be treated until the previous cohort has been fully evaluated for toxicity and a dose escalation decision has been made. Routine updates regarding patient and study status will be conducted.

Once the MTD is reached, the expansion component of the study will be completed to assess tolerability and efficacy. Patients in the phase II portion of the study will initiate study treatment at the MTD defined in the escalation component of the trial. Note that dose reduction within patients (individually) is allowed after the 4 week DLT observation period in the escalation and in the expansion components of the study (see Dose Modification guidelines, Section 8). Intrapatient dose escalation will not be allowed. Dose reduction will be required for a given patient in case of:

- ☐ Grade 3 or 4 toxicities
- Grade ≥ 2 elevation of creatinine, bilirubin, AST, or ALT lasting more than 14 days despite medical treatment, or
- Grade ≥ 2 ocular, skin or nail toxicity for more than 28 days in a row despite optimal medical treatment, or
- Grade ≥ 2 GI toxicity lasting more than 14 days despite medical treatment.

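### Section 7.5 gives two cut-offs for related Grade 3 fatigue, so an event of 7 to 14 days can be counted as a DLT or not

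*Combined protocol and SAP*

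**What the plan says.** Section 7.5 opens its DLT list for the idasanutlin arm with "Any of the following events that occur during cycle 1 (first 6 weeks) will be considered a DLT", provided the event is judged related to study treatment. Two entries in the table then deal with fatigue:

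- The general disorders row lists "Fatigue CTCAE Grade 3 for > 14 consecutive days".
- The last row, for other hematologic and non-hematologic toxicities, lists "Any other CTCAE ≥ Grade 3 toxicity except for" three exceptions. One of them is "Grade 3 fatigue for less than 7 days".

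Section 24.1 refers back to section 7.5 for the DLT definition and adds nothing on fatigue. Section 7.6 turns the count into a decision: "If no patient in the first cohort of 3 experiences a DLT, accrual will continue to test the next dose level". One DLT brings in three more patients at the same level, and two or more lead to de-escalation.

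**The concern.** Two durations are given for the same toxicity, and no rule says which prevails. A site could apply the fatigue row and record a 10-day event as no DLT. Another could apply the exemption, note that 10 days is not below 7, and record a DLT. The trial is open-label and multicenter, so without a rule the classification is made after the event, and possibly the rest of the cohort's results, are known. The Protocol Chair must be told of any DLT, but that depends on the site having already called the event one.

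At stake is the Phase Ib primary endpoint, and through it the MTD and the idasanutlin dose taken into Phase II. Fatigue is not a remote event here: sections 8.3.1 and 8.4.1 list it as an anticipated toxicity of idasanutlin and atezolizumab respectively.

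**Working it through.** The plan states no figure to reproduce on this point. The check has three parts: the two entries side by side, the dose decisions that depend on them, and an illustration of size.

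**1. Classification by duration (related Grade 3 fatigue)**

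| Duration | Fatigue row (DLT if > 14 days) | Catch-all, if it reaches fatigue (exempt if < 7 days) |
|---|---|---|
| 5 or 6 days | not a DLT | exempt, not a DLT |
| 7, 10 or 14 days | not a DLT | not exempt, a DLT |
| 15 days | DLT | DLT |

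The entries disagree where the duration is not above 14 and not below 7, that is, from 7 to 14 days inclusive.

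- *Reading 1: the catch-all covers only toxicities without a row of their own.* The fatigue row governs and a 7-14 day event is not a DLT. The fatigue exemption then has no function.
- *Reading 2: the exemption has effect.* The catch-all must then reach fatigue, a 7-14 day event is a DLT, and the 14-day row is redundant. Applied consistently, this would also void the duration limits for Grade 3 anemia, neutrophils, platelets, skin and AST/ALT.

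Each reading leaves some text without effect.

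**2. Effect of one extra DLT on the 3+3 decision (sections 7.6 and 24.1)**

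| Level | 0/3 to 1/3 | 1/3 to 2/3 | 1/6 to 2/6 |
|---|---|---|---|
| 1 and 2 | escalate becomes enter 3 more | enter 3 more becomes stop and go down | escalate (or accept as MTD if the next level was too toxic) becomes stop and go down |
| 3 | little effect | enter 3 more becomes stop, level 2 | MTD becomes stop, level 2 |
| -1 | little effect | enter 3 more becomes discontinue | MTD becomes discontinue |

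The two cells of little effect arise because section 24.1 requires at least 6 patients at the RP2D, so 3 more are entered either way. The event still counts towards the limit of 1 in 6. Counting levels 1 and 2 separately, the action changes in 6 + 2 + 2 = 10 of 12 cells. Nothing changes at 0/6 to 1/6, or once two DLTs have occurred. At the lowest level the consequence is the end of the cohort: "If the current dose level is at -1, the regimen will be considered too toxic".

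**3. Illustration with assumed rates**

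The documents give no rate for related Grade 3 fatigue of 7-14 days. With a per-patient DLT probability p, the chance of escalating past a level is (1-p)^3 + 3p(1-p)^5.

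| Assumed rate of other DLTs | 7-14 day fatigue not counted | adds 5 points | adds 10 points |
|---|---|---|---|
| 10% | 0.906 | 0.814 | 0.709 |
| 20% | 0.709 | 0.600 | 0.494 |

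These rates show sensitivity only and are not estimates for this trial.

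**The case against.** The strongest reply is that the wording does contain a precedence rule. The catch-all begins with the words "Any other CTCAE ≥ Grade 3 toxicity except for" and its row label also says *other*, so in ordinary reading the specific rows come first. A surplus exemption is weak evidence against this, because the GI exemption is equally surplus on Reading 1: diarrhea, nausea/vomiting and constipation all have their own rows. This stands in part. The two readings are not evenly balanced, and the fatigue row has the better claim. It does not close the matter, because the 7-day figure contradicts the row rather than merely repeating it, and the text does not show which number was intended.

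A second reply is that few patients would be affected. Section 3.7.2.3 reports DLTs only in blood, gastrointestinal and investigations classes among 99 single-agent idasanutlin patients. That is fair evidence against assuming a high frequency, although that study's DLT definition is not given and atezolizumab was not combined. The 10 of 12 count does not answer this reply: it reflects how sensitive any 3+3 design is to one event, and says nothing about how often such an event occurs.

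Third, each cohort is fully evaluated before the next opens (section 7.6), and the RP2D may be adjusted for tolerability (section 24.1). These steps soften the effect but supply no classification rule. The Protocol Chair's discretion in section 7.5 covers only lower-grade events that interrupt dosing. The wording of that interruption rule is a separate issue.

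A reader might also infer that fatigue is the only flawed exemption. The documents do not support that. The GI rows count Grade 3 or higher lasting at least 48 hours, for example "Diarrhea CTCAE Grade ≥ 3 for ≥ 48 hrs", whereas the exemption is limited to "Grade 3 diarrhea, nausea/ vomiting, or constipation for less or equal to 48 hours". A Grade 4 GI event under 48 hours is therefore not a DLT by its own row and not exempt in the catch-all, which is the same kind of ambiguity. Fatigue is distinct only in that its two durations differ.

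**Conclusion.** The inconsistency is real and limited. For related Grade 3 fatigue of 7 to 14 days inclusive, section 7.5 supports two classifications, with the wording leaning towards not a DLT. One such event can change an escalation, expansion or stopping decision. No frequency can be given, and the single-agent experience gives no sign that such events are common. It should be corrected in the next amendment, but it does not call the Phase Ib design into question.

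Two stronger conclusions might be drawn and are not supported. The first is that every 7-14 day event is a DLT because the lead-in counts any listed event; that ignores the word *other* in the catch-all. The second is that the 7-day split for fatigue in section 8.5 settles the threshold. That is a dosing rule, it measures time to resolution to Grade 1 or lower, and it does not define a DLT.

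**What to change.** Use one cut-off in both places.

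- **Default:** change the fatigue row to Grade 3 for 7 or more consecutive days, to match the existing exemption. The cost is a slightly stricter DLT definition.
- **If the clinicians prefer 14 days:** change the exemption to 14 days or less, and disclose the consequence. Under section 8.5, Grade 3 fatigue that takes more than 7 days to resolve to Grade 1 or lower requires stopping idasanutlin, so some patients would stop the drug for fatigue without counting as a DLT.

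For Phase Ib cohorts already evaluated, check for related Grade 3 fatigue of 7-14 days and record how each case was counted.

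Do not solve this with a general sentence confining the catch-all to toxicities without their own row. That would also remove from the DLT definition Grade 4 GI events under 48 hours, Grade 4 skin toxicity of 14 days or less, and Grade 3 alkaline phosphatase (whose row lists only Grade 4). The Grade 4 GI question needs its own clinical decision.

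The cost is one table line and a look-back at the adverse event records of at most 18 planned Phase Ib patients, with no added patients or assessments.

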# 7.6. Definition of Maximum Tolerated Dose (MTD) – for patients on idasanutlin arm only

The MTD will be defined as the highest dose tested in which a DLT is experienced by 0 out of 3 or 1 out of 6 patients among the dose levels. The first cohort of patients (3 patients) will be started at dose level 1, and each patient will be observed for 6 weeks on the specified dose:

If no patient in the first cohort of 3 experiences a DLT, accrual will continue to test the next dose level
If 1 patient experiences a DLT any given cohort/ dose level, an additional cohort of 3 patients will be treated at the same dose level
If 1 patient has a DLT out of 6 patients treated at this same dose, accrual will continue to test the next dose level
If 2 or more patients in 3 or 6 patients treated at a given dose experience DLT, the dose will be de-escalated to the next lower dose level. If the current dose level is at -1, the regimen will be considered too toxic and the corresponding cohort within the study will be discontinued
If 0 out of 3 or 1 out of 6 patients has a DLT treated at dose level 3, accrual will continue to the phase II portion of the study

No new cohort of patients will be treated until the previous cohort has been fully evaluated for toxicity and a dose escalation decision has been made. Routine updates regarding patient and study status will be conducted.

Once the MTD is reached, the expansion component of the study will be completed to assess tolerability and efficacy. Patients in the phase II portion of the study will initiate study treatment at the MTD defined in the escalation component of the trial. Note that dose reduction within patients (individually) is allowed after the 4 week DLT observation period in the escalation and in the expansion components of the study (see Dose Modification guidelines, Section 8). Intrapatient dose escalation will not be allowed. Dose reduction will be required for a given patient in case of:

- ☐ Grade 3 or 4 toxicities
- Grade ≥ 2 elevation of creatinine, bilirubin, AST, or ALT lasting more than 14 days despite medical treatment, or
- Grade ≥ 2 ocular, skin or nail toxicity for more than 28 days in a row despite optimal medical treatment, or
- Grade ≥ 2 GI toxicity lasting more than 14 days despite medical treatment.

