#### Phase Ib Trial of Idasanutlin and Atezolizumab 24.1.

For the dose-escalation study, a standard 3 + 3 dose escalation scheme will be utilized to evaluate the primary objective of determining a RP2D (Recommended Phase II Dose) for Idasanutlin in combination with Atezolizumab. Three dosing cohorts of Idasanutlin will be evaluated in combination with Atezolizumab (dosage will be held constant at 840 mg) to determine the RP2D and will occur in accordance with the dose escalation rule below.

1 Cycle = 28 days			
N of pts.	Dose Level	Atezolizumab (IV q15 days)	Idasanutlin (PO daily x 5 out of 28 days)
3-6	3	840 mg	200 mg
3-6	2	840 mg	150 mg
3-6	1	840 mg	100 mg
3-6	-1	840 mg	50 mg

DLTs are defined in section 7.5 and will be assessed during a DLT assessment window, which is during the first cycle of therapy. The RP2D from this study will be utilized in the Idasanutlin +

Atezolizumab arm in the Phase II portion of this study. The determination of the MTD and RP2D are reviewed in the following table. Of note, the PI may adjust the RP2D based on overall tolerability after cycle 1 at their discretion after discussion with all study Pl's.

Number of Patients with DLT at a given dose level	Escalation Decision Rule
0 out of 3	Enter 3 patients at the next dose level.  If dose level 3 is reached without DLT, then dose level 3 will be considered the MTD and RP2D.
>= 2	Dose escalation will be stopped. This dose level will be declared the maximally administered dose (highest dose administered), exceeding the MTD. Three (3) additional patients will be entered at the next lowest dose level if only 3 patients were treated previously at that dose.
	If this occurs at dose level 1, then 3-6 additional patients will be enrolled on dose level -1, based on toxicity occurring at that dose level. If ≥ 2 patients experience DLT at dose level -1, then the study is considered a failure.
1 out of 3	Enter at least 3 more patients at this dose level. If 0 of these 3 patients experience DLT, proceed to the next dose level. In the event that enrollment is on dose level 3 when this occurs, then dose level 3 is considered the MTD and the RP2D.
1 out of 3	If 1 or more of this group suffer DLT, then dose escalation is stopped, and this dose is declared the maximally administered dose. Three (3) additional patients will be entered at the next lowest dose level if only 3 patients were treated previously at that dose.

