≤1 out of 6 at highest dose level below the maximally administered dose	This is generally the MTD and RP2D. At least 6 patients must be entered at the recommended phase 2 dose. These patients will also be considered evaluable in the phase II portion of the study.

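### After a step-down, 7.6 lets a level passed on 0 of 3 stand as the idasanutlin Phase II dose, while 24.1 first requires 3 more patients there; no text says which rule governs

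*Combined protocol and SAP*

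**What the plan says.** **Section 7.6.** The MTD is the "highest dose tested in which a DLT is experienced by 0 out of 3 or 1 out of 6 patients". After 2 or more DLTs at a level, "the dose will be de-escalated to the next lower dose level"; no number of patients is given for that lower level. The section then states: "Patients in the phase II portion of the study will initiate study treatment at the MTD defined in the escalation component of the trial".

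**Section 24.1.** After 2 or more DLTs at a level, three "additional patients will be entered at the next lowest dose level if only 3 patients were treated previously at that dose". The level is generally the MTD and RP2D if there is at most 1 DLT "out of 6 at highest dose level below the maximally administered dose". The same table row adds: "At least 6 patients must be entered at the recommended phase 2 dose". Patients at that dose also count as evaluable in Phase II.

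**Top level.** On dose level 3 (200 mg) the sections agree. Section 7.6 gives the condition and its consequence together: "0 out of 3 or 1 out of 6 patients has a DLT treated at dose level 3, accrual will continue to the phase II". The first row of the 24.1 table says: "If dose level 3 is reached without DLT, then dose level 3 will be considered the MTD and RP2D".

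**Size.** The synopsis, Section 1 and Section 7.1 give 9 to 18 patients for Phase Ib.

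**The concern.** A level that was escalated past on 0 of 3 already meets the 7.6 definition of the MTD. When the next level up proves too toxic, a team working from 7.6 can declare the lower level the MTD at once and start Phase II. A team working from 24.1 must treat 3 more patients there first, and must step down again if 2 or more of the 6 have a DLT. This is one trial-level decision with two instructions, and no text gives either section precedence.

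It fixes the starting dose for an arm of up to 33 Phase II patients (24.3.1), in a combination whose safety is first tested in this Phase Ib. The evidence behind the dose differs too. By exact one-sided 95% limits, 0 of 3 excludes only DLT rates above 63%, 0 of 6 excludes rates above 39%, and 1 of 6 excludes rates above 58%.

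**Working it through.** **1. The plan's own size.** Under 7.6 a level left behind on 0 of 3 or 1 of 6 is never reopened, so level −1 is reached only if level 1 fails at the start. The longest path is three levels of 6, which is 18. The shortest path ending at level 3 is 3 + 3 + 3 = 9. The stated 9 to 18 therefore reproduces under 7.6.

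Under 24.1 a longer path exists:
- levels 1 and 2 each show 0 of 3;
- level 3 is expanded to 6 and fails;
- level 2 is filled to 6 and fails, then level 1 likewise;
- level −1 takes 6.

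The total is 4 × 6 = 24.

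**2. Worked case.** 100 mg 0/3, 150 mg 0/3, 200 mg 2/3.
- 7.6: 150 mg is the MTD after 9 patients, and Phase II opens there.
- 24.1: 3 more are treated at 150 mg. With at most 1 DLT among them, 150 mg stands (at most 1/6). With 2 or more, 150 mg is rejected and 100 mg is filled to 6. If no further DLT occurs, the RP2D is 100 mg after 15 patients.

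**3. Chance that the added cohort overturns a 0/3 level.** P(2 or more of 3) = 3p²(1 − p) + p³.

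| True DLT rate p | 10% | 20% | 30% | 40% |
|---|---|---|---|---|
| Overturned | 2.8% | 10.4% | 21.6% | 35.2% |

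**4. Whole escalation.** The documents give no DLT rates for the combination, so six sets are assumed for 50/100/150/200 mg. Each of the four levels can have two cohorts of 3, each with 0 to 3 DLTs, which gives 4⁸ = 65,536 combinations. Each is weighted by its binomial probabilities and run through both rules on the same patient sequence. Rule 7.6 accepts 0/3 or 1/6 with no added cohort. Rule 24.1 is taken literally: 0/3 is accepted at level 3, and lower levels are filled to 6 on step-down.

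| Assumed DLT rates, % | Step-down to 100 or 150 mg with only 3 treated | Final outcome differs | Mean Phase Ib size, 7.6 / 24.1 |
|---|---|---|---|
| 5/10/15/20 | 29.8% | 1.4% | 10.71 / 11.90 |
| 5/10/20/32 | 46.6% | 3.3% | 10.59 / 12.33 |
| 10/15/25/35 | 45.3% | 5.1% | 10.26 / 12.19 |
| 10/20/30/40 | 42.7% | 6.9% | 9.81 / 11.98 |
| 10/20/32/45 | 45.0% | 7.6% | 9.67 / 11.93 |
| 5/10/25/50 | 60.8% | 5.8% | 10.16 / 12.40 |

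- Outcome means the selected dose, or no dose. Rule 7.6 never ends lower than 24.1.
- The mean size difference is 1.2 (first set) to 2.3 (fifth set) patients.
- Under 24.1 the chance of more than 18 patients is at most about 0.3%.
- If level −1 is not filled to 6, the outcomes differ in 1.4% to 7.0% of trials.
- The selected dose rests on 3 patients in 71% to 76% of trials under 7.6, and in 5% to 38% under 24.1, all of the latter at level 3.

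**5. Sensitivity.** Other assumed sets give 1.0% (5/8/12/20), 3.4% (5/10/20/33), 7.3% (10/20/30/45) and 10.1% (15/25/40/55). A flat rate of 11/34, the DLT proportion on the earlier single-agent 5-day schedule (3.7.2.3), gives 10.3%.

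**The case against.** **The sections may be complementary.** The 7.6 step-down sentence is silent on numbers. From level 1 to level −1 it must mean treating new patients, since none has been treated at −1. Section 24.1 could then be supplying the missing detail. It also has a good claim to be the operative rule: it calls the scheme a standard 3 + 3, says escalation follows its own table, refers to 7.5 for DLTs but not to 7.6, and carries the RP2D into Phase II. This weakens the point. It does not remove it, because 7.6 accepts 0 of 3 outright and starts Phase II at that MTD, and no precedence is stated.

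**Safeguards exist.** Section 24.1 lets the RP2D be adjusted for tolerability after cycle 1, following discussion among the study PIs. Section 24.2 promises continuous toxicity monitoring. Section 7.6 requires individual dose reductions, and the DSMC reviews serious adverse events. The highest dose, 200 mg, is below the 250 mg single-agent MTD (3.7.2.7). These reduce the consequence, but none says whether 3 more patients must be treated first.

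**Stronger readings.** A reader might infer that identical data yield two different doses. They do not: on 0/3, 0/3, 2/3, Section 24.1 names no other dose but asks for 3 more patients, and the dose changes only if at least 2 of those 3 have a DLT. Nor is 30% to 61% a rate of wrong doses; it is how often the two instructions part. A reader might also call acceptance of 0 of 3 at level 3 an error. Section 7.6 and the first row of 24.1 agree on it, and the stated minimum of 9 fits. The sentence requiring at least 6 sits in a row about the level below the maximally administered dose, so its reach to level 3 is unclear rather than contradicted.

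**Conclusion.** The inconsistency is real and confined to the step-down: 7.6 can stop without the confirmatory cohort that 24.1 orders. Under the six assumed sets the conflict arises in 30% to 61% of trials, and the final outcome differs in 1.4% to 7.6%, always with 7.6 at the higher dose. Harsher assumptions take the difference to about 10%, and the mildest set tried gives 1.0%. These figures rest on assumed DLT rates and on the literal reading of 7.6 as adding no patients at a level already at 0 of 3. The effect on the final dose is modest, but the discrepancy runs toward less evidence and a higher dose, so it should be corrected before a step-down decision has to be made.

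**What to change.** In 7.6, adopt the 24.1 step-down rule: fill the lower level to 6, accept it if at most 1 of 6 has a DLT, and otherwise step down again. Name the RP2D as the Phase II starting dose. In the synopsis, Section 1 and Section 7.1, restate the Phase Ib maximum as 24.

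The cost is wording, about 1.2 to 2.3 more Phase Ib patients on average than under 7.6, and one further 6-week observation in the idasanutlin arm when the added cohort is needed. Added patients count toward Phase II if the dose is kept.

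Separately, and optionally, state whether the requirement for at least 6 patients at the RP2D applies at level 3. Requiring 6 there is a design choice; it would raise the minimum for a path ending at level 3 from 9 to 12 (3 + 3 + 6).
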